2.2.2 Inclusion criteria

All of these must be fulfilled at the time of screening assessment:

- 1- Age \geq 18 years (Operational definition: Patient's age on the day of eligibility screening.)
- 2- Admission to a critical care unit (Operational definition: Any unit where there is capability to administer invasive mechanical ventilation.)
- 3- Evidence of kidney dysfunction (Operational definition: serum creatinine \geq 100 $\mu\text{mol/L}$ [women] and \geq 130 $\mu\text{mol/L}$ [men] based on most recent bloodwork available prior to screening and that has not declined by $>$ 27 $\mu\text{mol/L}$ compared to the highest value recorded in the preceding 48 hours.)
- 4- Evidence of severe AKI based on at least one of the following three criteria:
 - i) \geq 2-fold increase in serum creatinine (sCr) from baseline (Operational definition: The baseline sCr is an *outpatient* reading within 365 days of the current admission date; if multiple pre-hospitalization values are available, the one closest to the date of hospital admission will be used. If an outpatient pre-hospitalization value is not available during the 365 days prior to admission date, the lowest creatinine value obtained during the current hospitalization should be taken as the baseline. This criterion is met if the current sCr is \geq 100% higher than the baseline value.)
 - ii) If current serum creatinine is \geq 354 $\mu\text{mol/L}$, this must be accompanied by evidence of a minimum increase of 27 $\mu\text{mol/L}$ from the baseline sCr. (Operational definition: If current sCr is \geq 354 $\mu\text{mol/L}$ and the patient has experienced an increase of 27 $\mu\text{mol/L}$ from the documented baseline, based on the definition delineated in i) for baseline sCr.)
 - iii) Urine output $<$ 6.0 mL/kg over the preceding 12 hours.

2.2.2.1 Rationale for inclusion criteria

The inclusion criteria are designed to identify a population of critically ill adults with severe AKI who have an increased likelihood of requiring RRT at some point during their hospitalization but who do NOT need immediate RRT at the time of eligibility assessment.

Criterion 3, Evidence of kidney dysfunction: This criterion will be used as an initial screen to identify patients with some degree of kidney dysfunction in whom RRT may be considered if the remainder of the criteria are met. It provides a useful entry point for coordinators to screen patients quickly and only consider individuals further if there is an elevation in sCr.

Criterion 4, Evidence of severe AKI: Determination of severe AKI will be grounded in the staging system outlined in the Kidney Disease Improving Global Outcomes (KDIGO) Guidelines for Acute Kidney injury.¹⁸ This classification system stages AKI into three levels based on the extent of sCr elevation in parallel with the degree and duration of oliguria; patients are classified based on the worst finding (either sCr or oliguria). In order to identify patients with severe AKI in whom RRT may be contemplated, patients must have evidence of at least Stage 2 AKI, which constitutes either a doubling of sCr or urine output < 0.5 mL/kg/hr x 12 hours (adapted to < 6 mL/kg over preceding 12 hours for ease of screening) or if the sCr is above 354 µmol/L at the time of screening, evidence that the sCr rose by at least 27 µmol/L from baseline.

2.2.3 Exclusion criteria

Any one of the criteria below would be grounds for exclusion:

- 1- Serum potassium concentration > 5.5 mmol/L (Operational definition: Based on last available bloodwork).
- 2- Serum bicarbonate concentration < 15 mmol/L (Operational definition: Based on last available bloodwork).
- 3- Presence of a drug overdose that necessitates initiation of RRT. (Operational definition: If noted in the chart or directly from the treating team as the primary reason for administering RRT.)
- 4- Lack of commitment to provide RRT as part of limitation of ongoing life support. (Operational definition: Critical care team has deemed the patient not to be eligible for escalation of life support, including the initiation of RRT, or substitute decision makers have declined offer of same.)
- 5- Any RRT within the previous 2 months. (Operational definition: If recorded in the medical chart by any clinician following the patient.)
- 6- Kidney transplant within the past 365 days. (Operational definition: As reflected in the medical chart.)
- 7- Known pre-hospitalization advanced chronic kidney disease, defined by an estimated glomerular filtration rate < 20 mL/min/1.73 m² in a patient who is not on chronic RRT. (Operational definition: The coordinator will review all documented serum creatinine values

within 365 days prior to the date of admission for the current hospitalization. The value closest to the admission date will be considered as the “baseline” and will be used to calculate the corresponding estimated glomerular filtration rate using an online calculator. A value of < 20 mL/min/1.73 m² derived from the CKD-EPI equation⁴² will be grounds for exclusion. The serum creatinine, age, sex, and race (Black/non-Black) is entered into a calculator found at: <http://www.qxmd.com/calculate-online/nephrology/ckd-epi-egfr>. It is expected that a large number of patients will not have readily available pre-hospitalization sCr data. In the case of a missing pre-hospitalization sCr, this exclusion criterion will be considered to have been NOT met.)

- 8- Presence or strong clinical suspicion of renal obstruction, rapidly progressive glomerulonephritis, vasculitis, thrombotic microangiopathy (eg, thrombotic thrombocytopenic purpura, hemolytic uremic syndrome, malignant hypertension, scleroderma renal crisis) or acute interstitial nephritis. (Operational definition: If explicitly described in the medical chart or strongly suspected as the cause of AKI by the clinicians following the patient.)

IF THE PATIENT MEETS ALL OF THE ABOVE INCLUSION CRITERIA AND NONE OF EXCLUSIONS 1-8, THEN THE PATIENT IS DEEMED PROVISIONALLY ELIGIBLE AND THE ATTENDING CLINICIANS WILL BE APPROACHED BY THE RESEARCH TEAM TO CONFIRM THEIR COMFORT WITH THE TRIAL ENROLLMENT USING THE TWO EXCLUSION CRITERIA DESCRIBED BELOW

- 9- Clinician(s) caring for patient believe(s) that immediate renal replacement therapy is absolutely mandated. (Operational definition: The study team will speak to the Critical Care attending physician, and at relevant sites, the Nephrology attending physician caring for the patient and ask if he/she agrees with the statement: “Renal replacement therapy must be initiated immediately in this patient.” If at least one of the clinicians answers “Yes”, the clinician will be asked to identify the primary reason for mandating the immediate start of RRT.)
- 10- Clinician(s) caring for patient believe(s) that deferral of renal replacement therapy initiation is mandated. (Operational definition: The study team will speak to the Critical Care and, at relevant sites, the Nephrology attending physician caring for the patient and ask if he/she agrees with the statement: “Renal replacement therapy must be deferred in this patient.” If at least one of the clinicians answers “Yes”, the clinician will be asked to identify the primary reason for mandating the delay in initiation of RRT.)

2.2.3.1 Rationale for exclusion criteria

Criterion 1: Hyperkalemia may predispose to dangerous cardiac arrhythmias. As a result, randomization of a patient with hyperkalemia to standard RRT initiation may be unethical.

Criterion 2: Severe metabolic acidosis may impair normal cell functions and compromise sensitivity to vasopressor agents in patients who are hemodynamically unstable. As a result, randomization of a patient with significant metabolic acidosis to a strategy of standard RRT initiation may be unethical.

Criterion 3: It is not ethical to withhold RRT in the presence of a dialyzable toxin.

Criterion 4: Severe irreversible acute or chronic illness leading clinicians to curtail or not escalate care is grounds for exclusion as it is unlikely that the timing of RRT initiation will have an impact on clinical outcomes in these individuals.

Criterion 5: The treatment effect of earlier RRT may be reduced by the receipt of any RRT in the preceding 2 months.

Criterion 6: The risk of acute graft rejection is greatest within 1 year following transplant and this condition is addressed primarily with enhanced immunosuppression.

Criterion 7: The prognosis of critically ill patients with severe chronic kidney disease may be disproportionately affected by chronic kidney disease rather than by the acute superimposed deterioration in kidney function (or any intervention for this deterioration) and such patients are routinely excluded from intervention trials in AKI.²⁰

Criterion 8: Since the prognosis of these conditions will largely be guided by ancillary therapies (e.g., relief of urinary obstruction, systemic immunosuppression), patients with AKI that is due to causes other than suspected acute tubular necrosis will be excluded.

Criteria 9 and 10: Even after all the above eligibility criteria have been satisfied, it is crucial for the relevant attending clinician(s) to be comfortable with randomization to either group as this reflects clinical equipoise.

Note regarding exclusions 9 and 10: Discussions with the attending physicians following the achievement of provisional eligibility are a crucial part of the enrollment process in this trial. Though patients may meet the study inclusion criteria and have none of exclusions 1-8, we are relying on clinician judgment to tell us whether a patient's condition mandates immediate RRT initiation or alternatively, if a patient's clinical condition is such that he/she is likely to have imminent kidney function recovery. Both such patients should be excluded from this trial.

This approach understandably entails some degree of subjectivity on the part of the attending physicians. The trial will allow clinicians to utilize a variety of clinical tools to make their determination, as no single biomarker has emerged as an adequately robust predictor of AKI progression and the subsequent need for RRT. In patients with oliguric AKI, a patient's response to a furosemide bolus is a frequently-employed prognostic tool of AKI progression in clinical practice; specifically, a limited response in terms of urine output (with varied definitions of what constitutes a "poor" response") might suggest the patient is likely to require RRT or have AKI that will not recover in the near future. This diagnostic strategy, named the "Furosemide Stress Test" has been standardized and evaluated by Chawla and Koyner et al.^{43,44} In preliminary studies, they have found that a urine output of < 200 mL in the 2 hours that follow an intravenous furosemide bolus has strong sensitivity and specificity for AKI progression. Though not mandated by the trial, clinicians wishing to risk stratify prospective trial participants using this technique will be asked to follow the method outlined in the published studies (provided in the study Operations Manual). For example, for a provisionally eligible patient who clinicians are reluctant to enroll in STARRT-AKI due to the possibility of imminent renal recovery, a low urine output in response to a furosemide

bolus (ie, a “positive furosemide stress test”) might change the physician’s impression regarding trial eligibility.

2.3 Trial intervention

2.3.1 Allocation of participants

Participants will be randomized 1:1 to accelerated vs standard initiation of RRT with variable block sizes and stratified by centre using a central randomization system that will be managed at the Applied Health Research Centre.

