2.10 Analysis plan

Baseline data will be summarized descriptively. The primary outcome of 90-day mortality will be evaluated using an intent-to-treat approach. A simple comparison of proportions will be performed using a chi-squared test. The risk ratio and relative risk reduction will be estimated with 95% confidence intervals. An adjusted analysis will also be completed using logistic regression and will include the following baseline variables: age, sex, sepsis, receipt of cardiopulmonary bypass and SOFA score.

The principal secondary outcome, the proportion of survivors who are RRT dependent at 90 days, presents challenges as the non-inclusion of participants who died might obviate the inter-group balance afforded by randomization. We will consider two complementary approaches to examine this question. First, we will use the adjusted model for the primary outcome to estimate the probabilities of 90-day survival. We will then use the reciprocals of these as weights in a logistic regression for RRT, resulting in an inverse probability weighted analysis. This is typically called a marginal structural model. The second approach will employ a multinomial regression model to jointly consider the states: dead at 90 days, alive at 90 days receiving RRT and alive at 90 days RRT-free. A similar approach will be used to estimate the probabilities of 365-day survival and to consider the states: dead at 365 days, alive at 365 days receiving RRT and alive at 365 days RRT-free.

Duration of ventilation, vasoactive therapy, ICU stay and hospitalization and albuminuria at 90 days (expressed as the urinary albumin to creatinine ratio in mg/mmol) will be compared by means of a t-test. Finally, eGFR decline of 25%, death in ICU, by 28 days and in-hospital, and ICU readmission and rehospitalization within 90 days will be compared by chi-squared tests.

Interim analyses for efficacy based on the primary outcome will be done when 25, 50 and 75% of planned enrollees have completed 90-day follow-up. Given the risks of false positive results with early stopping for benefit, statistical significance will be declared using small p-values established by O'Brien-Fleming boundaries on the primary outcome (90-day mortality). A detailed monitoring plan will be developed in consultation with the DSMB prior to commencement of recruitment.

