the ICU and/or nephrology attending physician and ask if they agree with the statement: "RRT must be initiated immediately in this patient" If the answer is "Yes", the patient will be excluded but may be rescreened for eligibility; and ● the clinicians caring for the patient believe that deferral of RRT is mandated. After fulfilling the above inclusion/ exclusion criteria, the study team will speak to the ICU and/or nephrology attending physician and ask if they agree with the statement: "RRT must be deferred in this patient" If the answer is "Yes", the patient will be excluded but may be rescreened for eligibility.

Randomisation, treatment allocation and blinding

Intervention

Patients enrolled in the STARRT-AKI trial will be randomly allocated to receive either accelerated (early) initiation of RRT, defined as start of RRT within 1 2 hours of fulfilling eligibility, or standard (delayed) initiation of RRT, whereby

RRT initiation is discouraged unless one or more clinical criteria for RRT develop and/or the attending physician determines that deferral of RRT is no longer in the patient's best interest. Eligible patients will be allocated 1 :1 by randomised permuted blocks (of variable size) and stratified by site, using a dedicated web-based platform.

Primary outcome

The primary outcome is all-cause mortality 90 days after randomisation.

[figure not shown]
Secondary outcomes

The secondary outcomes are:

- RRT dependence at 90 days after randomisation among surviving patients;
- composite of death and/or RRT dependence at 90 days after randomisation; ● composite of major adverse kidney events, defined as death, RRT dependence or sustained reduction in kidney function (defined as eGFR < 75% baseline eGFR) at 90 days after randomisation, 1 1 ● eGFR among surviving patients at 90 days after randomisation; ● albuminuria among surviving patients at 90 days after randomisation; ● death in the ICU, at 28 days after randomisation, and inhospital;
- RRT-free days to 90 days after randomisation; ● ventilator-free days and vasoactive therapy-free days to 28 days after randomisation; ● length of ICU stay and ICU-free days to 28 days after randomisation, ● length of hospitalisation and hospitalisation-free days to 90 days after randomisation; and ● health-related quality of life, using the EuroQoL EQ5D-5L scale, among surviving patients at 90 days after randomisation. 1 2

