The number and percentage of deaths through 90 days after randomisation will be reported for each treatment group. The primary effect estimate will be the relative risk of 90-day mortality, reported with 95% CI. The absolute risk difference and 95% CI will also be reported. Deaths up to 90 days after randomisation will be compared between the treatment groups using test. Additionally, the odds ratio (OR) (95% CI) will also be determined, primarily to permit comparisons between the primary unadjusted analysis and the various secondary pre-specified adjusted analyses of 90day mortality (Table 2).

Adjusted sensitivity analysis

Death at 90 days will also be analysed, adjusting for baseline characteristics (eg, age, sex, baseline eGFR, Simplified Acute Physiology Score [SAPS] II score at randomisation, surgical status, and presence of sepsis). Continuous variables (eg, age, eGFR and SAPS II score) will be modelled using restricted cubic splines with four knots to accommodate the possibility of non-linear relationships with the log odds of death. The OR and 95% CI will be determined first, primarily to permit comparisons between the unadjusted analysis and the secondary adjusted analyses of 90-day mortality. The adjusted treatment effect will be reported as the adjusted OR (95% CD. Should the adjusted OR be materially different from the unadjusted OR, a second adjusted model will be fit that employs the log link to provide adjusted estimates of the risk ratio. An additional sensitivity analysis will include site as a random effect in a generalised linear mixed model to assess if the variance component is important and affects inference.

Treatment of missing data

If more than 5% of patients from the ITT population are excluded from the adjusted analysis of the primary outcome due to missing data for baseline covariates, missing data will be imputed using fully conditional specification ²⁰ The imputation model will include all covariates required for the adjusted analysis as well as other baseline variables deemed related to the variables for which imputations are required. The multiple imputation will then be performed via chained equations to obtain ten imputed datasets. The adjusted analysis will be performed on the imputed datasets with the results appropriately pooled.

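### Randomisation is stratified by site, but the primary mortality test and its intervals ignore site, so they are mildly conservative to the extent that sites differ in mortality

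*Protocol*

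**What the plan says.** Both documents randomise within site. Protocol section 2.3.1 describes 1:1 allocation "with variable block sizes and stratified by centre using a central randomization system". The SAP, under Randomisation, treatment allocation and blinding, describes permuted blocks "stratified by site, using a dedicated web-based platform".

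The decisive analysis does not use that factor. Protocol section 2.10 states: "A simple comparison of proportions will be performed using a chi-squared test". The SAP's Principal analysis states: "The primary effect estimate will be the relative risk of 90-day mortality, reported with 95% CI". It adds a risk difference with its interval, and it refers to "comparisons between the primary unadjusted analysis and the various secondary pre-specified adjusted analyses", so the unadjusted result is plainly the primary one. (The name of the test is lost from the SAP text available here; chi-squared is taken from the protocol.)

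Site is not among the protocol's adjusting variables ("age, sex, sepsis, receipt of cardiopulmonary bypass and SOFA score"), nor among the examples in the SAP's Adjusted sensitivity analysis. It appears once, at the end of that SAP section: "An additional sensitivity analysis will include site as a random effect in a generalised linear mixed model".

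**The concern.** Permuted blocks within site keep the arms nearly equal inside each site. A site with high mortality then contributes almost equally to both arms, and its level largely cancels from the arm difference. The pooled chi-squared test and the unadjusted intervals take their variance from the overall death proportion, which still contains the between-site component. Where sites differ, the quoted standard error exceeds the true one.

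This is separate from the choice of prognostic covariates. It concerns analysing by the one factor on which the trial restricts its randomisation. The SAP (Trial sites) expects about 170 sites in 15 countries, so some variation in mortality is plausible. Precision also matters if the result is null, because Protocol section 1.1 says that a finding of no superiority would be used to support the conservative strategy.

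**Working it through.** **Inputs from the documents.** 40% against 34% mortality, two-sided 0.05, power 0.90, 1,359 per arm, 2,780 after interim looks, and 2,866 after 3% crossover and dropout (Protocol 2.9). Final level 0.044 and extension to at least 3,000 patients (SAP, Analysis principles and Sample size).

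**Assumed, because the documents do not give them.** The between-site share ρ of the variance of 90-day mortality, the block sizes, and the spread of site sizes.

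**The plan's own figures.** With pooled variance,
n = [1.960·√(2×0.37×0.63) + 1.282·√(0.40×0.60 + 0.34×0.66)]² / 0.06² = 1,358.6, so 1,359 per arm. Then 2,780/0.97 = 2,866. Both reproduce. Integrating over the four SAP thresholds gives an overall two-sided level of 0.0499, and power of 0.901 at 2,780.

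**True against quoted variance.** Under blocking within site,
true variance = quoted variance × [1 − ρ + ρR],
where R is the sum of squared site imbalances divided by N. In simulations with unequal site sizes and block mixes of 2/4, 4/6 and 4/6/8, R was 0.03 to 0.07 for 100 to 170 sites. Incomplete blocks therefore change little, and the quoted standard error is too large by about 1/√(1 − ρ).

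**True size.** 2·[1 − Φ(2.014/√(1 − ρ))], where 2.014 is the two-sided 0.044 critical value.

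**Power at 2,866.** The null standard error is s0 = √(4×0.37×0.63/2866) = 0.01804. The alternative standard error is s1 = √(2×(0.24 + 0.2244)/2866) = 0.01800.
- Unstratified: Φ[(0.06 − 2.014·s0)/(s1·√(1 − ρ))]. At ρ = 0 this is Φ(1.315) = 90.6%.
- Site-stratified with 1% of information lost in small sites: Φ[(0.06 − 2.014·s0·g)/(s1·g)], where g = √((1 − ρ)/0.99).
- Patient equivalent: the extra patients at which the unstratified test, under the same blocked randomisation, reaches the stratified test's power.

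| Share ρ | SE too large by | True size | Power, unstratified | Power, stratified | Gain (points) | Patients |
|---|---|---|---|---|---|---|
| 0 | 0% | 0.044 | 90.6% | 90.3% | −0.3 | none |
| 1% | 0.5% | 0.043 | 90.7% | 90.6% | −0.1 | none |
| 2.1% | 1.1% | 0.042 | 90.8% | 90.9% | 0.1 | 8 |
| 5.4% | 2.8% | 0.038 | 91.2% | 91.8% | 0.6 | 67 |
| 9.7% | 5.2% | 0.034 | 91.7% | 92.9% | 1.3 | 146 |

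The last three shares correspond to site log-odds standard deviations of 0.3, 0.5 and 0.7, that is, 10th to 90th percentile site mortality of 31–49%, 26–55% and 21–61%. The table takes R = 0; with R of 0.04 to 0.07, the excess at ρ = 10% is 5.0% to 5.2%. The two tests break even at ρ of about 1.6%.

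**Cross-check.** Direct simulation (6,000 trials per setting, 170 sites, blocks of 2/4/6) gave power for chi-squared against Cochran-Mantel-Haenszel of 90.6 and 90.1 at SD 0, 90.4 and 90.8 at SD 0.3, 91.2 and 91.8 at SD 0.5, and 90.5 and 91.6 at SD 0.7. The loss when sites do not differ is thus 0.3 points by formula and 0.5 by simulation, or about 0.4. At 3,000 patients, 170 sites and blocks of 2/4, the unstratified test has 91.9% to 92.8% power for ρ of 1% to 10%.

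**The case against.** The best defence is that nothing here is invalid. The SAP promises an overall type I error of at most 5%, and a conservative test keeps that promise. The unadjusted test is simple and transparent, the SAP does look at site through its mixed model, and at small ρ a stratified test gains nothing. The protocol names chi-squared, and the SAP (23 May 2019) post-dates the third interim analysis (24 April 2019), so changing the decisive statistic is more than a wording edit. All of this stands, and it limits the weight of the point.

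It does not remove the point. The mixed model checks whether the site variance matters, but the SAP sets no rule for what follows. Its conditional odds ratio also corrects neither the primary p-value nor the relative-risk and risk-difference intervals.

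Three stronger readings are tempting and unsupported:
- **Too many false positives, or an underpowered trial.** The error runs in the other direction, and power exceeds 90% throughout the table.
- **A standard error that is too large whatever the data.** The excess is zero if sites do not differ, and the documents do not say how much they do.
- **A loss worth about 280 patients at ρ = 9.7%.** The sum 2,866 × [0.99/(1 − 0.097) − 1] = 276 measures information gained over a trial without blocking. The planned test already benefits from the blocking through its smaller true variance, so the fair figure is about 145.

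**Conclusion.** The mismatch between randomisation and primary analysis is real, and its direction is certain wherever sites differ. Its size is modest and rests on an assumed between-site share. For 1% to 10%, the standard error is about 0.5% to 5% too large, and the true size of the nominal 0.044 test is about 0.043 to 0.034. The power given up at 2,866 is about 0 to 1.3 points, equal to roughly 10, 65 and 145 patients at shares of 2.1%, 5.4% and 9.7%. These figures treat the final test as a single look at 0.044 and assume a 1% information loss from small sites. This is a point about precision and interval width; it does not threaten the trial's validity.

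**What to change.** In the SAP's Principal analysis:
- Pre-specify a Cochran-Mantel-Haenszel test stratified by site, with the Mantel-Haenszel relative risk and risk difference and variances suited to sparse strata.
- Fix in advance a rule for pooling sites that lack both arms, for example within country.
- State that the final 0.044 level applies to this statistic, and record that the change was made blind to outcomes by arm.
- Keep the unstratified chi-squared test as a sensitivity analysis.

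At minimum, keep chi-squared as the decisive test, say that it is knowingly conservative, and report stratification-aware intervals for the relative risk and risk difference beside it.

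No new data are needed. The costs are about 1% of information in small sites (about 0.4 points of power if sites do not differ) and a documented departure from the test named in Protocol section 2.10.
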